11.3.2 Safety Analysis of Laboratory Data

Laboratory data, which includes CBC, BUN, creatinine, and liver function tests, will be examined in different ways. Descriptive statistics (means, standard deviations, medians and ranges) at pre-infusion, and at 1, 2, 4, 6 weeks post- T-cell infusion will be calculated. Laboratory data collected at 3-month intervals for the first year will also be summarized. A scatter diagram depicting laboratory values at each time point for each subject will also be generated. In order to analyze changes in laboratory values, a shift table with Stuart-Maxwell chi-square analysis of the change in the normal range from pre-infusion to post infusion time points (using high, normal, low) will be performed. When appropriate, these tables are collapsed and the McNemar's test applied in place of the Stuart-Maxwell test. These statistical tests will be primarily performed for the overall subject group.

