4.1.2 ATLCAR.CD30 Cells Administration

Post ASCT, once the subject has started to experience hematologic recovery (defined as ANC \geq 500 cells/mm3 for 3 consecutive days, AND platelet count \geq 25

cells/mm3 without transfusion over the preceding 5 days, AND Hg \geq 8g/dL without transfusion support over preceding 5 days), ATLCAR.CD30 cells will be administered as described below. The dose of cells and exact day of cell infusion will vary, depending on the cohort enrolled. See section 4.1.3 for dose levels and dose escalation rules. This will generally occur between 14 and 20 days following infusion of autologous stem cells following high-dose chemotherapy.

Premedication

Subjects may be pre-medicated with Benadryl (diphenhydramine) up to 1 mg/kg IV (max 50mg) and Tylenol (acetaminophen) 10 mg/kg oral (max 650mg). Alternative antihistamines or anti-pyretics can be used in the case of diphenhydramine or acetaminophen hypersensitivity. We will premedicate subjects who have a history of reactions to blood products. Steroids should be avoided given their detrimental effect on the survival of the infused T cells (see exclusion criteria 5). Anti-emetics in appropriate dosage for each subject will be prescribed as necessary.

Cell Administration

ATLCAR.CD30 cells will be given by a licensed provider via intravenous injection over 1-10 minutes through either a peripheral or a central line. The expected volume will be 1-50cc.

Monitoring

Monitoring will be undertaken according to institutional standards for administration of blood products. Subjects will be monitored for at least 4 hours post infusion.

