- Screening includes tests to confirm eligibility for both procurement and treatment; NOTE: some pre-infusion screening tests may not be performed until the day of infusion. A window of +/-3 days will apply to all study visits for the first 8 weeks unless otherwise noted below. A window of +/-10 days will apply to every 3 months study visits, and a window of +/-30 days will apply to visits separated by ≥ 6 months. Yearly follow-up visits during long-term follow-up for a total of 15 years. *An annual physical exam will be required ONLY for the first 5 years of follow up. NOTE: Follow-up visits for month 3 and beyond can be conducted locally (i.e., by local health care provider, local oncologist, etc.). The study team would continue to contact the subjects at the long-term follow-up points and request they visit their local healthcare provider to complete the follow-up test and assessments, where applicable. The study team would collect clinical information, tests and assessments results, other clinical observations from the subject's medical record and their local health care provider.
- 2. Serum pregnancy testing will be done in female subjects of childbearing potential within 72 hours prior to procurement and repeated 72 hours prior to infusion.
- 3. Medical history must include collecting the following information: 1. New malignancy(ies) 2. New incidence or exacerbation of pre-existing neurologic disorder 3. New incidence or exacerbation of a prior rheumatologic or other autoimmune disorder 4. New incidence of a hematologic disorder and 5. New incidence of infection (potentially product related).
- 4. PFTs = pulmonary function tests and includes forced expiratory volume in 1 second (FEV1), forced vital capacity (FVC) and diffusing capacity (DLCO); EF=ejection fraction evaluated via MUGA or ECHO. These will be evaluated within 3 months prior to transplant.
- 5. CBC includes complete blood count with diff and platelets. *NOTE: Preprocurement, only Hg is necessary, and if a serum Hg has already been performed within 7 days of procurement as part of SOC pre-transplant work-up, it does not need to be repeated. Prior to ATLCAR.CD30 treatment, CBC with diff and platelets must be performed within 24 hours prior to infusion. CBC with diff and platelets performed as needed on D1/Week 3.

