- c. **RCR:** For replication competent retrovirus (RCR) testing, subject blood samples will be collected and stored pre-infusion. The pre-infusion sample will only be tested if the subject develops a long-term gene therapy side effect as described in Section 7.5.2. Additional samples for RCR testing will only be collected and subsequently analyzed in the event that the subject develops a long-term gene therapy side effect as described in Section 7.5.2.
- d. Cytokine Testing: Serum collected before and 3-4 hours after infusion for cytokine testing.
 - 12. Serum from blood drawn for functional studies at baseline and week 6 will be stored for measurement of human anti-mouse antibodies (HAMA). These studies will be performed in the event of a suspected immunologic reaction. See section 7.5.4 for additional details.
 - 13. Data on all adverse experiences/toxicities per CTCAE v4.0 regardless of seriousness must be collected for documentation purposes only for 6 weeks after dosing of the study drug/biologic. Adverse event data collection will cease in subjects that receive any other hemopoietic cell product or receive therapy for relapse of their primary malignancy. Data on disease status will continue to be collected as appropriate.

- a. If CRS signs and symptoms occur (see APPENDIX VIII- CRS Toxicity Grading Scale and Management Guidelines), a serum sample (~1 mL) for IL-6 analysis and 20 mL of blood should be collected before instituting treatment for CRS. Subsequent 20 mL blood samples should be collected once a day for the first 3 days. At the discretion of the sponsor, a daily sample may be requested for an additional 4 days. See section 7.5.6 for additional details.
- b. Serum (~1 mL) and 20 mL of blood should also be collected in the event of serious toxicities that develop that require hospitalization. Subsequent 20 mL blood samples should be collected once a day for the first 3 days. At the discretion of the sponsor, a daily sample may be requested for an additional 4 days. See section 7.5.6 for additional details.
- c. An additional blood sample of approximately 20 mL may be collected if any subject develops an AE or event of clinical significance that is thought to be at least possibly related to the CAR T cells.
 - 14. CoA generated at completion of required studies for production/QA of cells.

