5.2 Inclusion Criteria Prior to Infusion of ATLCAR.CD30 Cells

- 1. Informed consent explained to, understood by and signed by subject/guardian; subject/guardian given copy of informed consent.
- 2. 3 to 17 years of age for pediatric subjects, ≥18 years of age for adults; NOTE: children will not be allowed to enroll in a dose cohort until a minimum of 2 adult subjects were enrolled and complete their DLT assessment follow-up at that dose level.
- 3. Diagnosis of recurrent HL with a treatment plan that will include high dose chemotherapy with/without total body irradiation and autologous cell transplantation.
- 4. NHL subjects with ALK negative CD30+ anaplastic large-cell lymphomas, CD30+ ALCL regardless of ALK status, with chemotherapy-sensitive relapse, CD30+ highrisk DLBCL, CD30+ cutaneous T cell lymphoma, or CD30+ mycosis fungoides who are otherwise eligible for transplant, are eligible for this study.
- 5. CD30+ disease (result can be pending at the time of cell procurement, but must be confirmed prior to treatment with ATLCAR.CD30 cells); NOTE: CD30+ disease requires documented CD30 expression by immunohistochemistry based on the institutional hematopathology standard.
- 6. Evidence of adequate organ function as defined by:

The following is required prior to infusion of ATLCAR.CD30 cells:

• Absolute neutrophil count (ANC) ≥500 cells/mm3 for 3 consecutive days; Note: ANC may be measured at the beginning and the end of a time frame expanding at least 3 days and does not need to be evaluated on each individual day **AND**

- Platelet count ≥25,000 cells/mm3 without transfusion over preceding 5 days; Note: Platelets may be measured at the beginning and the end of a time frame expanding at least 5 days and does not need to be evaluated on each individual day **AND**
- Hg \geq 8g/dL without transfusion support over preceding 5 days; Note: Hg may be measured at the beginning and the end of a time frame expanding at least 5 days and does not need to be evaluated on each individual day
- Bilirubin ≤ 1.5 times the upper limit of normal (ULN)
- AST \leq 3 times ULN
- Serum creatinine ≤1.5 times ULN
- Pulse oximetry of > 90% on room air
- 7. Imaging results from within 60 days prior to transplant (used as baseline measure for documentation of disease status).
- 8. In women of child-bearing potential (WOCBP), a negative serum pregnancy test within 72 hours prior to procurement and again 72 hours prior to infusion is required.

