9.0 ADVERSE EVENTS

9.1 Definitions

9.1.1 Adverse Event (AE)

An adverse event (AE) is any untoward medical occurrence (e.g., an abnormal laboratory finding, symptom, or disease temporally associated with the use of a drug) in a subject or clinical investigation subject administered a pharmaceutical product and which does not necessarily have a causal relationship with this treatment. An AE can therefore be any unfavorable and unintended sign (including an abnormal laboratory finding), symptom, or disease temporally associated with the use of a medicinal product, whether or not related to the medicinal product.

Hospitalization for elective surgery or routine clinical procedures that are not the result of an AE (e.g., surgical insertion of central line) need not be considered AEs and should not be recorded as an AE. Disease progression should not be recorded as an AE, unless it is attributable by the investigator to the study therapy.

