11.3 Data Analysis Plans

11.3.1 Safety Analysis of Adverse Event Data

All subjects who received the ATLCAR.CD30 infusion will be included in the safety analysis. Adverse event data and corresponding toxicity grades six weeks after T-cell infusion and during long-term follow-up will be summarized in the form of tables. Incidence tables will be generated to summarize incidence of subjects reporting at least one episode of each specific adverse event, incidence of adverse events causing withdrawal and incidence of serious adverse events. The total number of episodes for each event reported (Frequency Table), the severity and attribution to study therapy of each episode reported (Severity Table and Attribution Table) will also be displayed.

Listings of adverse events by subjects will include the time to onset, the duration of each event, the severity of each event, and the relationship of the event to study therapy, whether it was a serious event, and whether it caused withdrawal. Safety data will be summarized for the overall subject group and by dose levels.

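### For ANC, platelets and hemoglobin, the planned high/normal/low shift test cannot register further worsening in a subject already low at infusion, and no planned table compares later grade with the subject's own baseline grade, chiefly at months 3-12

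*Combined protocol and SAP*

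**What the plan says.** Section 11.3.2 classifies each laboratory value as high, normal or low and plans a Stuart-Maxwell "analysis of the change in the normal range from pre-infusion to post infusion time points (using high, normal, low) will be performed", or McNemar's test where tables are collapsed, mainly in the pooled group. It gives no significance level and does not say whether McNemar is uncorrected, corrected or exact. It also plans descriptive statistics before infusion and at weeks 1, 2, 4 and 6, and a per-subject scatter diagram. In addition, "Laboratory data collected at 3-month intervals for the first year will also be summarized".

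The baseline is close to infusion: footnote 5 of the Time and Events Table (section 4.2) says "CBC with diff and platelets must be performed within 24 hours prior to infusion". Section 4.1.2 times infusion "once the subject has started to experience hematologic recovery", generally 14 to 20 days after stem cell infusion. The section 5.2 floors are ANC 500 cells/mm3, hemoglobin 8 g/dL and "Platelet count ≥25,000 cells/mm3 without transfusion over preceding 5 days". (Section 4.1.2 prints a different platelet figure. The two must be reconciled, but this point does not depend on it.)

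Footnote 13 of the same table says that data on all toxicities, whether serious or not, "must be collected for documentation purposes only for 6 weeks after dosing of the study drug/biologic". The table's toxicity row ends at week 6. CBCs continue at months 3, 6, 9 and 12.

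**The concern.** This concerns three counts only: ANC, platelets and hemoglobin. A subject can enter the shift table already low, and low is one cell however deep the count goes. The test then sees such a subject only if he or she improves. Expected recovery after transplant supplies improvements whatever the cells do, and there is no control arm to subtract it.

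This is the only inferential analysis planned for blood counts, in a trial whose primary objective is safety and tolerability. Read alone, a significant shift toward normal could be taken as hematologic safety. The timing matters because the rationale for Amendment 6, which took hematologic events out of the DLT definition, describes hematologic toxicity from CAR-T as delayed by months rather than weeks. It also calls these cytopenias manageable and not apparently linked to significant adverse events. At months 3-12 no planned output sets a subject's grade beside the grade at infusion.

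**Working it through.** **Inputs from the documents.** Three categories and two tests (11.3.2); entry floors (5.2); 12 to 18 subjects (11.2); required visits at weeks 1, 2, 4 and 6, week 3 being optional (4.2).

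**Assumptions.** No values in the high category; threshold p<0.05; a range for the share low at baseline. The plan states none of these, so both versions of McNemar are shown.

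**Step 1: what the test uses.** Stuart-Maxwell and McNemar use only off-diagonal cells. In a trial table, changing the low-to-low cell from 8 to 0 left the Stuart-Maxwell statistic at 3.636. If all 18 subjects start low, stay low and each worsens by one grade, there are no discordant pairs: Stuart-Maxwell cannot be computed and exact McNemar gives p=1.0.

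**Step 2: formulas.** With two occupied categories Stuart-Maxwell reduces to uncorrected McNemar. For d falls (not low to low) and u recoveries (low to not low):
- uncorrected: (d-u)²/(d+u) on 1 df;
- exact: p = 2 × Σ C(d+u, k)/2^(d+u), summed over k = 0 to min(d,u).

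| d | u | chi-square | p, uncorrected | p, exact |
|---|---|---|---|---|
| 3 | 0 | 3.00 | 0.083 | 2/8 = 0.25 |
| 4 | 0 | 4.00 | 0.046 | 2/16 = 0.125 |
| 6 | 0 | 6.00 | 0.014 | 2/64 = 0.031 |
| 9 | 0 | 9.00 | 0.003 | 2/512 = 0.004 |
| 6 | 1 | 25/7 = 3.57 | 0.059 | 2×8/128 = 0.125 |
| 9 | 2 | 49/11 = 4.45 | 0.035 | 2×67/2048 = 0.065 |
| 9 | 5 | 16/14 = 1.14 | 0.285 | 2×3473/16384 = 0.42 |

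The values are the same with d and u exchanged.

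**Step 3: best case for detecting worsening** (every not-low subject falls, nobody recovers). The numbers not low, for n=12 / n=18, are 6 / 9 if 50% start low, 4 / 6 if 67%, and 3 / 4 if 75% (rounded down). Uncorrected p is 0.014 / 0.003, 0.046 / 0.014 and 0.083 / 0.046. Significance needs at least 4 not-low subjects uncorrected, so it is out of reach once 12-3 = 9 of 12 or 18-3 = 15 of 18 start low. Exact needs 6, so the limits become 12-5 = 7 of 12 and 18-5 = 13 of 18. Recoveries raise the bar: with 0, 1, 2 or 3 recoveries, uncorrected McNemar needs at least 4, 7, 9 or 11 falls.

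**Step 4: the reassuring direction.** With no falls among not-low subjects, a significant shift toward normal needs 4 recoveries uncorrected (4/12 = 33% or 4/18 = 22% of subjects) or 6 exact (6/12 = 50% or 6/18 = 33%). Five are not enough for exact (2/32 = 0.0625). Subjects who stay low do not enter the calculation.

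**Step 5: an illustration.** Take 18 subjects, all low at infusion: 6 recover to normal, 6 deepen within low, 6 are unchanged. The planned comparison gives exact p=0.031, toward improvement. A sign test on change in grade (6 better, 6 worse) gives p=1.0. With 12 subjects split 4/4/4 the figures are 0.125 and 1.0.

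**The case against.** The best reply is that nobody needs to read the shift test alone. Through week 6, abnormal laboratory findings can be adverse events, toxicities are CTCAE-graded, and section 11.3.1 puts them into severity tables and by-subject listings, so severe early falls should appear. Later, the history must ask about new hematologic disorders, delayed adverse events are recorded and tabulated, and with 12 to 18 subjects the scatter diagram shows each fall. No dose decision uses the test: hematologic toxicity is outside the DLT definition in section 4.1.3. All of this stands and limits the harm. It does not make the test informative for these counts, and it supplies no comparison of a subject's later grade with his or her own baseline grade.

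Two further objections also stand. The p-values depend on a McNemar version and a threshold that the plan does not name. And CBCs are not scheduled for everyone through month 12: under section 4.1.4, subjects who progress after the 6-week assessments or receive other therapy move to Appendix IV, whose table has no CBC and no month 9 column. A grade table at months 3-12 would therefore describe a shrinking group selected for not having progressed.

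A reader might infer that the test is invalid, that it can never detect worsening, or that the trial cannot see deepening cytopenia. The documents support none of these. The limit lies in the categories and in confounding by recovery. Subjects who start normal and fall do register, and the raw values remain in the plots and summaries.

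**Conclusion.** The point holds as a moderate weakness that is cheap to repair. For ANC, platelets and hemoglobin, worsening from an already low baseline cannot enter the planned test, and a significant shift toward normal may mainly reflect transplant recovery. That part is structural. How often it bites depends on the share low at infusion, which the documents do not give; early timing and low entry floors make a substantial share plausible, but that is a judgement. Assuming a 0.05 threshold, nominal reassurance needs four one-way recoveries uncorrected or six exact. The missing comparison matters chiefly at months 3, 6, 9 and 12, when CBCs are drawn on the main schedule but routine adverse-event collection has ended. The dose-finding result is not affected.

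**What to change.** In section 11.3.2 add, for ANC, platelets and hemoglobin, a descriptive CTCAE v4.0 shift table of baseline grade against:
- worst grade in weeks 0-6;
- grade at week 6;
- grade at months 3, 6, 9 and 12.

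Report the number and percentage worsening by at least one grade, and to grade 3-4, with exact 95% confidence intervals, overall and by dose level. At each time point show the number with a CBC as the denominator and the number without one, by reason, and state that the month 3-12 rows describe only subjects still on the main schedule. Keep the planned high/normal/low table, but state that for these three counts its p-value is not evidence of hematologic safety.

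The text should admit the new table's limits:
- There is no control for post-transplant recovery.
- Worst of several visits against one baseline favours apparent worsening. With no true change and an assumed 5-10% chance per visit of reading one grade worse, independently, the four required visits show 1-0.95⁴ = 19% to 1-0.90⁴ = 34% of subjects as worse. The single-visit rows should be read beside it.
- Intervals are wide: 2/12 = 17% (2-48%), 2/18 = 11% (1-35%), 0/18 = 0% (0-19%), and wider where denominators shrink.
- A fall within one grade is still not shown.
- Denominators after week 6 are selected by progression.

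The cost is a paragraph of analysis-plan wording and one table program. It needs no extra blood draws because it uses only CBCs already scheduled.

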11.3.3 Analysis of Expansion and Persistence of Transduced T Cells

The frequency of T cells transduced with the vector (T cells expressing will be summarized at pre and post-infusion time points using mean \pm SD, medians and ranges to evaluate their expansion and persistence. Changes in each of these T cells from pre-infusion to each time point of post-infusion will be assessed and compared using paired t-tests, or when appropriate, the Wilcoxon signed ranks test. Paired comparisons of these T cells within a subject at each time point will also be performed. These analyses will be performed in the overall subject group.

Plots of growth curves will be generated to graphically illustrate patterns of T-cell expansion. Plots will be generated to depict patterns of survival and expansion of T cells for each of the two vectors. Longitudinal modeling techniques such as the random coefficient mixed model will be employed to model each of the repeatedly-measured T cells. These models account for variation in individual-level intercepts and slopes over the follow-up time. Thus, we will be able to model proliferation of T cells over time and estimate the magnitude of expansion or decline of T cells. We will include dose level as an independent variable in the model to account for different doses received by subjects.

Alternative strategies to analyze these outcomes include calculation of area under the curve over time for T cell frequencies or piecewise longitudinal models based on apparent trends from plots of growth curves. Despite the small subject numbers, a datadense study will be generated due to the repeat measurements on proliferation, immune function, etc. on each subject. The modeling strategies proposed here are amenable to these types of data but will however be considered exploratory and interpreted with caution due to limited study power.

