1.6 Study Design and Rationale

ASCT may be the only curative option for subjects with refractory/relapsed hematological malignancies. Despite ASCT, disease recurrence remains the major cause of treatment failure. Hence development of non-toxic consolidation treatments after transplant remains a highly desirable objective, and the adoptive transfer of CTLs is one promising approach [64-67].

In this Phase I multicenter study, peripheral blood will be collected for production of ATLCAR.CD30 cells in subjects with CD30⁺ lymphoma at high risk of relapse post-transplant, and scheduled to undergo ASCT. Three dose levels will be evaluated to identify the MTD in this population: Level $1 = 2 \times 10^7 \text{ CAR}^+ \text{ T cells/m}^2$; Level $2 = 1 \times 10^8/\text{m}^2$; Level $3 = 2 \times 10^8/\text{m}^2$. The total number of cells infused will be calculated on the number of CAR-T cells as requested by the FDA. Similar to the prior phase I

LCCC1524-ATL
Administration of T lymphocytes Expressing the CD30 Chimeric Antigen Receptor (CAR)
for Prevention of Relapse of CD30+ Lymphomas after High Dose Therapy and Autologous
Stem Transplantation (ATLAS)
ATLCAR.CD30

summarized in section 1.5.5, we will monitor the persistence of these infused cells in the peripheral blood of the subjects and whenever lymph nodes are biopsied as per routine clinical care during the first year after treatment at the tumor site by measuring the level of the transgene by both phenotypic and molecular analyses. Currently, we can regularly detect a single transduced cell in 50,000 peripheral blood mononuclear cells by real-time PCR amplification. Moreover, because gene persistence and expression may not correlate with antitumor effector function, we will also determine the functionality of the peripheral blood T cells *ex vivo*.

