Ex vivo expanded, polyclonally activated T cells have been infused as early as two days after stem cell transplant in myeloma subjects without significant side effects [68]. However, since the study we propose will be the "first in man" application of ATLCAR.CD30⁺ T cells after ASCT, we will infuse these cells after ASCT once hematologic recovery is evident (see section 4.1.2 for this definition). By using this conservative approach, we believe we will be able to infuse T cells in an environment in which homeostatic mechanisms favor lymphoid expansion [69] without interfering with stem cell engraftment. It is now evident that non-myeloablative conditioning is required to allow high level expansion of CAR-T cells and obtain optimal anti-tumor efficacy [70, 71]. ASCT creates a lymphodepleted environment, with production of high levels of homeostatic cytokines such as IL-7 and IL-15 that induce expansion of the infused CAR-T cells in the absence of competing endogenous lymphoid cells for the homeostatic cytokines [69].

The ability to combine CAR-based therapies with ASCT will reduce tumor immune evasion of this cell therapy. Tumor cells use several mechanisms to evade immune responses, by generating hostile chemokine and cytokine milieus or by recruiting inhibitory cells such as Tregs and Th2 cells. This may limit the benefits of CAR-based therapies [72]. ASCT depletes Tregs and disrupts the tumor microenvironment improving the prospects for CAR⁺T cell persistence, expansion and anti-tumor activity. HL and ALCL in particular will provide a useful model for studying this postulate since HL and ALCL cells release inhibitory molecules and ligands (TGF β , IL-10, Fas-L) and attract suppressive T-cell subsets including Th2 and Tregs [73, 74].

As outlined above, toxicities and even deaths [45, 69] due to "tumor lysis syndrome" and "cytokine storms" have occurred in subjects with high tumor burden when they received CAR-T cells. This is likely the result of rapid and massive T-cell activation through their CAR/costimulatory molecule complex followed by the release of cytokines (IFN γ , TNF α , IL-6 etc.). These potentially lethal toxicities should be limited if CAR-T cells are infused after ASCT, since the burden of targeted tumor will be minimized. [44, 45]. We will collect serum before and after infusion for cytokine monitoring, and continue to monitor subjects for 4 hours after infusion.

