3.2 Secondary

- 3.2.1 PFS is defined from day of ASCT to relapse (in subjects with a documented complete response after ASCT) or progression (in subjects with documented stable disease or partial response after ASCT), or death as a result of any cause as per the Revised Response Criteria for Malignant Lymphoma (see APPENDIX II-Revised Response Criteria for Lymphoma) [74].
- 3.2.2 Overall survival will be measured from the date of administration of CAR.CD30 transduced ATL to date of death.
- 3.2.3 Persistence of CAR.CD30 T cells in vivo will be determined by quantitative PCR and flow cytometry in peripheral blood samples.

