7.3 Short-term Follow-up

7.3.1 D1 Week 1

Clinical evaluation: History, physical examination

Laboratory studies:

- CBC with differential and platelets
- CMP: BUN, creatinine, Na, K, Cl, CO2, glucose, calcium, albumin, total protein, total bilirubin, ALT, AST, alkaline phosphatase
- Blood Sample for Correlative Studies (see section 7.5)
 - Function and persistence studies
 - Quantitative PCR
 - Cytokine testing
 - Genetic analysis (see Section 7.5.5)
Toxicity: Toxicity will be assessed according to the NCI CTCAE v. 4.0, CRS Toxicity Grading Scale (See APPENDIX VIII- CRS Toxicity Grading Scale and Management Guidelines).

Patient reported outcome questionnaires for adult subjects (optional): PROMIS Global Health Scale, PROMIS Physical Function, and selected questions from NCI PRO-CTCAE

7.3.2 D1 Week 2

Clinical evaluation: history, physical examination, Karnofsky or Lansky performance status.

Laboratory studies:

- CBC with differential and platelets
- CMP: BUN, creatinine, Na, K, Cl, CO2, glucose, calcium, albumin, total protein, total bilirubin, ALT, AST, alkaline phosphatase
- Blood Sample for Correlative Studies (see section 7.5)
 - Function and persistence studies
 - Quantitative PCR
 - Cytokine testing
 - Genetic analysis (see Section 7.5.5)

Toxicity: Toxicity will be assessed according to the NCI CTCAE v. 4.0, CRS Toxicity Grading Scale (See APPENDIX VIII- CRS Toxicity Grading Scale and Management Guidelines).

Patient reported outcome questionnaires for adult subjects (optional): PROMIS Global Health Scale, PROMIS Physical Function, and selected questions from NCI PRO-CTCAE

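### Section 11.3.3 reads post-infusion change in the relative frequency of transduced T cells as expansion or decline, while the host-cell denominator is expected to rise after ASCT; absolute counts can be derived through month 12

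*Combined protocol and SAP*

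**What the plan says.** Section 3.2.3 defines the endpoint by assay, without a unit: "Persistence of CAR.CD30 T cells in vivo will be determined by quantitative PCR and flow cytometry in peripheral blood samples". Measuring the survival of the cells in vivo is a secondary objective (Section 2.2.1).

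The units that do appear are ratios: copies per µg DNA (Section 4.2, footnote 11a; Section 7.4), percent (Sections 7.4 and 7.5.3), and the stated sensitivity, which is to "detect a single transduced cell in 50,000 peripheral blood mononuclear cells" (Section 1.6).

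Section 11.3.3 takes frequency as the analysis variable: "The frequency of T cells transduced with the vector (T cells expressing will be summarized at pre and post-infusion time points". (Text is missing after the open bracket; nothing here depends on it.) The variable goes into paired tests, growth-curve plots and a random-coefficient model, and an alternative is the "calculation of area under the curve over time for T cell frequencies". From the model the plan concludes that "we will be able to model proliferation of T cells over time and estimate the magnitude of expansion or decline of T cells". One covariate is named: "We will include dose level as an independent variable in the model to account for different doses received by subjects".

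On the host, Section 1.6 states that "ASCT creates a lymphodepleted environment", and Section 4.1.2 puts the infusion generally at day 14-20 after the stem cells. Section 7.3 lists "CBC with differential and platelets" at the follow-up visits, but Section 11.3.2 uses the CBC only for safety summaries and shift tables. No section converts frequency to cells or copies per volume of blood.

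**The concern.** Expansion and decline are statements about the number of cells. A frequency tracks number only if its denominator is stable. In this trial the protocol itself expects the denominator to move: the product is given into a lymphocyte-poor host, chosen because conditions then favor lymphoid growth. As the host's own cells return, the frequency of transduced cells falls even if their number does not.

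The error runs in one direction, so a subject whose lymphocytes recover quickly will seem to have poorer expansion. Random intercepts and slopes do not remove it, because each subject's recovery is absorbed into that subject's reported slope. At stake are the expansion and decline estimates for a secondary objective, and the integration-site analysis in Section 11.3.5, which relates integration location to expansion and persistence.

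**Working it through.** The plan states no expected fold change, power or precision for persistence, so there is no figure of its own to reproduce.

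**Identity.** Frequency = CAR-T number / denominator count. Between two visits, therefore:

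apparent fold = true fold / denominator fold.

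**Inputs.** The analysis variable and its interpretation come from Section 11.3.3, the host state from Section 1.6, the timing from Section 4.1.2, and N = 12-18 from Section 11.2. The denominator rise is an assumption; the hematologic criteria for infusion cover neutrophils, platelets and hemoglobin, not lymphocytes.

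**Apparent fold by assumed denominator rise.**

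| True change in CAR-T number | 1.5-fold | 2-fold | 3-fold | 5-fold |
|---|---|---|---|---|
| constant | 0.67 | 0.50 | 0.33 | 0.20 |
| 2-fold rise | 1.33 | 1.00 | 0.67 | 0.40 |
| 5-fold rise | 3.33 | 2.50 | 1.67 | 1.00 |

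At a 2- to 3-fold rise a constant number appears as a fall of 1 - 0.50 = 50% to 1 - 0.33 = 67%, and a true doubling appears as no change or a one-third fall.

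**The denominator depends on the assay.** Suppose lymphocytes go from 0.2 to 1.5 x10^9/L. A lymphocyte-gated flow percentage then has a denominator rise of 1.5 / 0.2 = 7.5. If the PCR DNA comes from mononuclear cells and monocytes stay at 0.5, the rise is (1.5 + 0.5) / (0.2 + 0.5) = 2.0 / 0.7 = 2.9, and a constant CAR-T number appears to fall by 1 - 1/2.9 = 65%. All these counts are assumptions. If DNA is taken from whole blood, neutrophil recovery adds to the dilution.

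**Illustrative effect on a slope test.** A simulation used per-subject slopes on the log10 scale at weeks 0, 1, 2, 4 and 6, a two-sided 5% t-test, 20,000 runs, between-subject slope SD 0.05 log10 per week and residual SD 0.3 log10. Both SDs are assumed.

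| True CAR-T change | Host rise | Result on the frequency scale | N=12 | N=18 |
|---|---|---|---|---|
| constant | 2-fold | significant decline | 51% | 70% |
| constant | 3-fold | significant decline | 88% | 98% |
| 2-fold rise | 3-fold | significant decline | 21% | 31% |
| 2-fold rise | 3-fold | significant rise | about 0% | about 0% |

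On the absolute scale, a constant number gives a significant decline in about 2.5% of runs, and a true doubling is detected in about 51% (N=12) or 71% (N=18). These absolute-scale runs include no extra error from the blood count, so they are somewhat favorable.

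**Where the correction can be computed.** In Table 4 the CBC with differential is scheduled pre-infusion, at weeks 1, 2, 4 and 6 and at months 3, 6, 9 and 12, as needed at the optional week 3 visit, and not in the later six-monthly or yearly columns. Correlative samples do appear in those later columns. Appendix IV lists correlative samples and no CBC. There is no CBC at the 3-4 h draw, but one is required within 24 hours before infusion (Section 4.2, footnote 5).

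**The case against.** Several points on the other side stand.

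- **The paired test is largely safe.** Pre-infusion transgene should be close to zero, so dilution can shrink the pre- to post-infusion change or push it below detection, but should not reverse it. A reader might infer that the whole of Section 11.3.3 is invalid; the text does not support that.
- **Absolute counts cannot replace frequency throughout.** A reader might assume that every input is already collected. It is not: after month 12, and in Appendix IV follow-up, samples are drawn without a scheduled CBC.
- **The size is not in the documents.** The 7.5-fold example above gives an 87% fall for a lymphocyte-gated percentage, but it should not be carried over to PCR on mononuclear cells. Nor is the 2 to 59 fold range in Section 1.5.1 a true absolute fold that can be divided by a denominator rise: it is itself a rise in PCR signal.
- **The units are partly inferred.** Copies per µg and percent appear in sampling rules, and assay detail sits in a Laboratory Manual that is not among the documents. Still, Section 11.3.3 uses frequency both for the summaries and for the AUC.
- **Dose comparisons.** Dose level is a covariate and random intercepts absorb some baseline difference, so a claim that dose comparisons are broadly distorted would go too far.

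The plan also labels the modeling exploratory and urges caution because power is limited. That caveat covers imprecision. It does not cover a bias with a known direction, and the objection does not remove that.

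**Conclusion.** The concern holds for post-infusion trajectories through month 12: growth curves, random-coefficient slopes, AUC and comparisons with the 3-4 h sample. As measures of CAR-T number they are biased downward by the factor by which the denominator rises. The direction follows from arithmetic and from the protocol's own account of the host at infusion. The size rests on an assumed recovery, 50-67% for a constant number at a 2- to 3-fold rise, and the simulated rates rest on assumed SDs and a log-linear course.

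Dose escalation and the MTD do not use these data. This is an inexpensive improvement to a secondary objective, not a flaw in the trial's main purpose.

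**What to change.** In Section 11.3.3, for visits from infusion through month 12 where a CBC with differential exists, pre-specify absolute circulating CAR-T:

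- **Flow:** CAR-positive percentage x count of the gated parent population.
- **qPCR:** copies per µg DNA converted to copies per volume of blood, using the count of the cells from which the DNA was extracted. The DNA mass per cell enters as a constant and cancels from folds and log slopes.
- **3-4 h sample:** use the pre-infusion CBC taken within 24 hours.

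Fit the expansion slope, growth curve and AUC to log absolute values, and report relative frequency alongside. Keep relative frequency as the measure for persistence after month 12 and for Appendix IV follow-up, and leave the thresholds that trigger sampling as they are.

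Cost: plan wording and a derived variable, with no new blood draws. The drawbacks are added error from the blood count, no absolute value at week 3 if no CBC is drawn, and none after month 12 or after a switch to Appendix IV follow-up. The flow parent gate and the qPCR DNA source must be taken from the Laboratory Manual and stated in the plan.
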